**K. PROCEDURES FOR REPORTING ANY DEVIATIONS FROM THE ORIGINAL STATISTICAL PLAN**

All deviations observed and/or achieved from the statistical plan mentioned above will be presented, justified and their impact analyzed, in the study report.

**L. IN THE CASE OF MULTICENTRE INVESTIGATIONS, MINIMUM AND MAXIMUM NUMBER OF SUBJECTS TO BE INCLUDED FOR EACH CENTRE**

Not applicable, CI is monocentric.

**8. DATA MANAGEMENT**

**A. DATA ENTRY AND COLLECTION METHODS**

The data will be collected from the patient records in the paper CRF directly by the investigator. The CRF data will then be entered into a database by a representative of the sponsor.

In accordance with applicable laws and regulations, data confidentiality will be ensured by appropriate security means:

- Patients will be identified in the CRF and the clinical database by a numerical identifier combining the number of the center and the number of the patient. Only the centres will keep a confidential list of included patients that will link the patient's ID to their identity.
- No personal data will be collected.

## **B. PROCEDURES FOR EXAMINING DATA, CLEANING UP DATABASES, AND ISSUING AND RESOLVING DATA QUERIES**

The data will be collected from the CRFs into the study database directly in the investigator center during a monitoring visit. At a minimum, the date of collection of the CRF or the request and the identification number of the subject will be reported. A form collecting the CRFs entered will be signed by the monitor and countersigned by the investigator to attest to the integrity of the data entered.

Data entry may result in requests for clarification called "queries", to which the investigator will respond by confirming or modifying the data concerned. These requests for clarification are annexed to the CRF at the investigator and the sponsor.

## **C. PROCEDURES FOR VERIFYING, VALIDATING AND SECURING ELECTRONIC CLINICAL DATA SYSTEMS**

### **i. GENERAL**

In order to ensure the verification, validation and security of the electronic systems generating, or managing the clinical data entered into the above-mentioned database, SERF has put in place the following elements:

- Update monitoring system;
- Host proxy system;
- Individual workstations equipped with anti-virus software with automatic updates;
- Locking, password access and encryption of mobile workstation partitions;
- Triple level of backups: real-time synchronization of virtual machines, backup to a production server and daily encryption and transfer to a backup hosting site;
- Secure erasure of SERF disks prior to disposal by physical destruction;
- Network protected by a security box (VPN).

### **ii. SPECIFIC**

Backups are encrypted by private keys, and access to the study's production server is protected by NTFS rights.

Clinical data is hosted on the same server as the rest of the SERF information system, but accessible only by the sponsor's clinical department staff and hierarchy.

Access to the clinical data entry system is through username/password authentication. Passwords are controlled for complexity and should be changed regularly. 5 unsuccessful attempts block access to the account.

Any connection to the system and any changes in clinical data are recorded for the duration of the study.

## **D. MAINTAINING CONFIDENTIALITY AND RESPECTING THE PRIVACY OF SUBJECTS**

The confidentiality of the subjects will be ensured by pseudonymization using a patient number (with 3 incremented digits) assigned to the person who is willing to participate in the research and communicated on all the documents necessary for the research; or by erasing by appropriate means nominative data on copies of source documents, intended for research documentation.

## **E. DATA RETENTION**

The investigator should maintain all study documents in accordance with Good Clinical Practice and regulations. The records will be kept until SERF authorizes their destruction. If the investigator declines this responsibility, the retention of records will be assigned to an individual who accepts this responsibility. In the event of a transfer of responsibility or place of storage, the sponsor must be informed in writing.

Data archiving after the completion of the study will be performed in accordance with SERF procedures for archiving clinical data from an investigation. The database that gave rise to the statistical analysis will also be locked and archived by the person responsible for the analysis (paper or computer).

## **F. RETENTION PERIOD**

In accordance with Annex XV Chapter 3.3 of Regulation (EU) 2017/745 on medical devices, which sets out the retention period by the sponsor and the investigator of the documents and data, the data retention period shall be 15 years after the end of the investigation.

## **G. OTHER ASPECTS OF CLINICAL QUALITY ASSURANCE**

In accordance with the General Data Protection Regulation, an impact assessment of the study will be carried out by SERF; The study will also be registered in a specific register.

In addition, as part of the implementation of its quality management system, an internal SERF auditor may be required to carry out an audit of the investigating centre. This audit will ensure compliance with the procedures envisaged by this protocol during the conduct of the investigation.

The health authorities may also be required to carry out audit activities of the investigating centre.

## **9. AMENDMENTS TO THE CLINICAL INVESTIGATION PLAN**

All amendments to the protocol will be made known to all investigators involved in the research. Amendments will be notified to the competent authorities and the Ethics Committee in accordance with the regulations in force.

Investigators sign each amendment prior to implementation and after approval by any authority that previously approved the protocol. Finally, the investigators undertake to respect the content.

Any amendment that modifies the coverage of the subjects or the benefits, risks and constraints of research will be the subject of a new information letter and the signing of a non-opposition form, the collection of which follows the same procedure as that mentioned in the chapter 13.

## **10. DEVIATIONS FROM THE CLINICAL INVESTIGATION PLAN**

### **A. STATEMENT THAT THE INVESTIGATOR IS NOT AUTHORIZED TO DEVIATE FROM THE ICP**

The investigator is not allowed to deviate from the Clinical Investigation Plan, except in the context of protecting the subject's rights, safety, and well-being under emergency conditions. In this case, any deviations must be documented and forwarded to the sponsor as soon as possible.

### **B. PROCEDURE FOR RECORDING, REPORTING AND GAP ANALYSIS IN RELATION TO THE CIP**

This study will be carried out in accordance with the requirements of the protocol. Any deviation from these criteria will be justified and carefully documented. The deviation will be considered a major deviation and considered for the final analysis of the study if it relates to any of the following:

- Information and consent procedure;
- Inclusion/non-inclusion criteria.
- Follow-up visit not carried out;

- Primary outcome.

Major deviations from the protocol will be recorded and will be mentioned in the final report. In the event of a discrepancy in the subject's information or consent, the investigator must immediately correct the deviation by following the steps outlined in Chapter 13. In all cases, the investigator should justify the deviation during a monitoring visit, by means of the appropriate documentation.

### **C. NOTIFICATION REQUIREMENTS AND DEADLINES**

Notification of a deviation from the protocol must be communicated to the sponsor as soon as possible via letter, email or any other means of communication containing the justification and documentation relating to the deviation.

### **D. CORRECTIVE AND PREVENTIVE ACTIONS AND CRITERIA FOR DISQUALIFICATION OF THE PRINCIPAL INVESTIGATOR**

At the first major deviation, intentional or unintentional - except for cases of protection of patients' rights, safety and well-being - observed by the sponsor, a reminder of the procedures to be followed will be made to the investigator and/or members of the investigating team.

## **11. DEVICE ACCOUNTING**

Article R1121-3-1 of the Public Health Code only provides for the free supply of devices in cases of interventional research. As the study is carried out after obtaining the CE marking and the device is used for its intended use, the requirements of this chapter do not apply.

### **A. ACCOUNTING PROCEDURE**

Not applicable.

### **B. PROCEDURES AND INSTRUCTIONS FOR THE RETURN OF POTENTIALLY HAZARDOUS DEVICES**

Not applicable.

## **12. DECLARATION OF CONFORMITY**

### **A. DECLARATION OF HELSINKI**

The study will be conducted in accordance with the ethical principles that are set out in the Declaration of Helsinki.

## **B. COMPLIANCE WITH ISO 14155 NF AND NATIONAL AND/OR REGIONAL REGULATIONS**

The study will be conducted in accordance with the International Conference on Harmonization for Good Clinical Practice (ICH/GCP) transposed into the ISO 14155:2020 Standard. It will be carried out in accordance with applicable European, national and local regulatory requirements. The information of subjects and the processing of data will be carried out in accordance with Regulation 2017/745 on medical devices, the Data Protection Act of 6 January 1978 in its latest version in force and the General Data Protection Regulation (EU) 2016/679 of 27 April 2016.

In accordance with the regulations, a data controller is the referent:

[name], the data controller

Email: [[contact]](mailto:[contact]) or [[contact]](mailto:[contact])

## **C. APPROVALS/FAVOURABLE OPINIONS REQUIRED**

The investigation is considered a 4.1 case study according to the French national classifications from the ANSM. Consequently, an application must be submitted to a CPP and the ANSM. Validation by a CPP and compliance with the MR001 reference methodology are required prior to the start of the study.

## **D. ADDITIONAL REQUIREMENTS**

Any additional requirements on the part of the Committee for the Protection of Persons or the ANSM will be respected and implemented before the start of the investigation.

## **E. INSURANCE**

This study is a non-interventional post-marketing study. As such, the sponsor of the study, SERF, in accordance with the legislation in force, is not obliged to take out specific insurance for research.

## **F. INVESTIGATIVE FUNDING**

The financing plan for the study is drawn up separately from the protocol.

# **13. PROCESS FOR OBTAINING NON-OPPOSITION**

## **A. GENERAL PROCESS FOR OBTAINING INFORMED CONSENT**

Informed consent is mandatory for studies meeting the Reference Methodology MR-001.

Prior to the first inclusion and in compliance with good clinical practices, the study investigator(s) are trained by the sponsor in the patient information process as well as in the collection of informed consent during the study set-up visit.

During a patient's visit planned as part of the systematic follow-up of hip replacements, the investigator offers to participate in HF if he or she meets the selection criteria.

To do this, the investigator provides the information relating to the oral test and gives the information letter (see Appendix 3). The investigator also answers any questions he may have. After the subject has been able to consider all the information and has been given the newsletter, and after the reflection period that has been given to him, he then has the choice to give his consent to his participation in the study and the collection of his data. The patient will be able to give consent from the moment he has received all the information until his next follow-up visit.

If the investigator expresses his or her consent, he or she obtains the consent in the form provided (see Appendix 3), of which he or she keeps the copy that he or she has imperatively dated and signed, in the investigator's binder, *and also gives a copy to the subject*. The patient is then included in the HF and considered as a "subject" participating in the HF. *The patient has time to think about it after the presentation of the study to give his or her agreement or not to his participation.*

A copy of the newsletter is given to the subject.

## B. SPECIAL CASES

No special case is envisaged because the study is carried out in routine care.

# 14. ADVERSE EVENTS, ADVERSE DEVICE REACTIONS, AND DEVICE DEFECTS

The term 'complications' used by the investigators includes the different definitions of event, adverse reaction, expected or not, serious or not, and dysfunction.

## A. DEFINITIONS OF ADVERSE EVENTS AND ADVERSE REACTIONS TO THE DEVICE

**Adverse event (AE):** any adverse event, unintentional illness or injury, or adverse clinical signs, including an abnormal laboratory finding, in participants, users, and others, in the course of a clinical investigation, whether or not related to the device under clinical investigation

**Serious Adverse Event (SAE):** any adverse event that resulted in:

- Death.
- A serious deterioration in the participant's state of health, which is the cause:
  - o a life-threatening illness or injury, or
  - o a permanent impairment in anatomical structure or function, or
  - o hospitalization or prolongation of the patient's hospitalization, or
  - o a medical or surgical procedure to prevent any life-threatening illness or injury or permanent impairment of anatomical structure or function, or
  - o of a chronic disease.
- Fetal distress, death of the fetus, congenital physical or mental impairment, or birth defect.

A planned hospitalization due to a pre-existing condition or a procedure required by the clinical investigation plan, without a serious deterioration in health, is not considered a serious adverse event. As a reminder, the definitions applicable in the context of medical device vigilance (corresponding to post-marketing surveillance of medical devices).

**Serious incident:** any incident that has directly or indirectly caused, likely to have resulted or likely to result in:

- The death of a patient, user, or any other person,
- A serious deterioration, temporary or permanent, in the state of health of a patient, a user or any other person,

A serious threat to public health.

**Serious Adverse Device Reaction (SAE):** An adverse reaction to the device that results in one of the characteristic consequences of a serious adverse event.

**Unexpected serious adverse reaction of the device (EIGID):** a serious adverse reaction of the device whose nature, impact, severity and consequences have not been identified in the current risk assessment.

## B. DEFINITION OF DEFECTS AND MALFUNCTIONS OF THE DEVICE

**Malfunction:** Failure of the medical device under investigation to function in accordance with its intended use when used in accordance with the instructions, clinical investigation plan, or investigator's brochure.

**Device Defect:** Any defect in the identity, quality, durability, reliability, safety, or performance of a device under investigation, including any malfunction, misuse, or defect in the information provided by the manufacturer.

**Incident:** any malfunction or alteration of the characteristics or performance of a device made available on the market, including an error in use due to ergonomic features, as well as any defect in the information provided by the manufacturer and any undesirable side effects.

**Serious incident:** any incident that has directly or indirectly caused, likely to have resulted or likely to result in:

- The death of a patient, user, or any other person,
- A serious deterioration, temporary or permanent, in the state of health of a patient, a user or any other person,
- A serious threat to public health.

## C. EVENTS, SERIOUS ADVERSE REACTIONS, SERIOUS ADVERSE REACTIONS TO THE DEVICE, SERIOUS UNEXPECTED ADVERSE REACTIONS TO THE DEVICE, PUBLIC HEALTH THREATS

See Chapter B.

## D. LIST OF UNDESIRABLE REACTIONS THAT MAY NOT BE REPORTED

Only events that are not causally related (see below) to the device being investigated, comparator, or investigation procedure may not be reported to SERF.

Causality is determined by the definitions below:

Unbound	

- No temporal link,

- Does not follow a known and biologically improbable DM reaction pattern,

- Interruption/reduction and reintroduction does not affect SAE,

- Site or organ not affected by the MD or procedure,

- Other cause identified,

- SAE not related to a misdiagnosis result by the MD in HF.

Possible	Weak link but cannot be totally excluded (includes cases for which causality cannot be assessed or no information could be obtained)
Probable	The link seems relevant and/or no other cause can explain the SAE
Causal link	

- Temporal link,

- Known side effect for this category of MD or this type of procedure,

	

- Known DM reaction pattern,

- Site or organ affected by the MD or procedure,

- Interruption/reduction and reintroduction affects SAE,

- Possible other causes have been excluded,

- SAE due to a user error,

- SAEs related to a misdiagnosis result by the MD in HF.

--	--

In all other cases:

- Any **serious adverse event** (SAE) with a proven or reasonably foreseeable causal link;
- Any **defect or malfunction or incident** of a device that could have resulted in a SAE in the absence of appropriate measures or intervention, or if the circumstances had been less favourable;
- Any **new information** concerning the 2 previous points,

The investigator reports the complication to the sponsor according to the deadlines and procedures provided for below.

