Secondary outcome(s)	
The survival rate by component as well as the survival rate by etiology will be determined according to the Kaplan-Meier all-cause curve.
 
The safety of the implants will be evaluated by the occurrence of adverse events related to the medical device. These elements will be sought by the clinical examination of the practitioner and the radiological examination, carried out as part of routine practice.
 
Patient satisfaction with their hip replacement will be assessed using a satisfaction questionnaire.
 
Implant performance will be assessed through the Harris Clinical Hip Score (HHS) and Forgotten Hip Score (SHO-12).

Description of the study population	
Between January 2016 and December 2018, about 120 patients were operated on with a SAGITTA® EVL R revision femoral stem at the Rouen University Hospital – Charles Nicolle Hospital. All patients with a SAGITTA® EVL R revision femoral stem will be seen again at a medium-term postoperative follow-up visit (minimum 4 years postoperatively). During this follow-up, they will be offered to participate in this clinical investigation.

Criteria for Inclusion of Subjects	
 
- Patient of legal age on the date of surgery,
 
- Patient implanted with a SAGITTA® EVL R revision femoral stem as part of its indications between 01/01/2016 and 31/12/2018,
 
- Patient with a health insurance scheme
 

Criteria for non-inclusion of subjects	
 
- Patient who has not expressed consent to the collection of his/her data and participation in the study,
 
- Patient unable to understand the surgeon's instructions or perform postoperative follow-up.
 

	

- Patient with a contraindication to the use of the SAGITTA® EVL R revision femoral stem

- Patient implanted with a SAGITTA® EVL R revision femoral stem outside of their indication

Number of Subjects	As the study is descriptive, there is no calculation of the number of subjects needed according to a hypothesis. All patients operated on at the Rouen University Hospital – Charles Nicolle Hospital and with a SAGITTA® EVL R femoral stem will be included. This represents about 120 patients.

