## B. EXPECTED ADVERSE REACTIONS

Known side effects (or complications) related to the use of SAGITTA® EVL R rods or the surgery required for their implantation are identified in the device's instructions for use and listed below:

- Allergy to the various materials that make up the implant and/or surgical equipment, in particular to metal,
- Pseudarthrosis, osteolysis, loosening of the prosthesis,
- Instability, dislocation, insufficient range of motion,
- Deformation, cracking or breakage of a component,
- Bone fracture,
- Collapse, migration, shortening or lengthening of the operated limb,
- Infection, sepsis,
- Delayed healing,
- Local, transient or permanent nerve damage,
- Cardiovascular disorders (hematoma, deep vein thrombosis), pulmonary embolism,
- Urinary tract infection,
- Deep abscess, fistula,
- Deterioration of the femoral and acetabular implant by stem/acetabulum contact during movements of extreme amplitude, mechanical noise may be heard when walking,
- The friction of components with each other can generate wear debris, corrosion or the release of metal particles that can induce a local reaction of the tissues,
- Residual hip pain.

*Notes:*

*Some of these complications can lead to prolonged operating time, revision surgery, or implantation failure/postponement of surgery.*

*It should be noted that any joint prosthesis is subject to wear and tear that can force the surgeon to operate again.*

*The surgeon is responsible for complications that may result from an incorrect prescription, a defective operating technique or a lack of asepsis. In no case can these complications be attributed to SERF.*

In addition, situations with an increased risk of failure are also listed:

- Severe muscular, neurological or vascular impairments affecting the affected extremity,
- Destruction, loss or poor bone quality that can affect the stability of the implant (for reasons of fatigue resistance), severe osteoporosis, significant deformities of the joint to be replaced,
- Any associated conditions that could compromise the function or implantation of the prosthesis,
- Systemic or metabolic disorders,
- Intellectual inability of patients to understand the surgeon's instructions,
- Drug addiction, alcohol, tobacco or drug abuse,
- Local bone tumors that may affect the stability of the implant,
- Obesity, overweight, high patient activities, intensive sports practices, patients with balance disorders,

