### ii. SECONDARY OBJECTIVES

The secondary objectives of this study are to:

- Study survival rates by components and etiology (revision and revision with reconstruction)
- Studying patient satisfaction with their hip prosthesis
- Confirm the safety of these implants by studying any complications observed
- Evaluate performance through the clinical scores of HARRIS (HHS) and forgotten prosthesis score (SHO-12) of femoral stems SAGITTA® EVL R.

The criteria for each of the objectives are presented in Chapter 6.A.iii.

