#### **Complications**

All complications (events, adverse reactions and dysfunctions, serious or not, expected or not; see definitions in the chapter 0) observed since the implantation of the SAGITTA® EVL R rods for each subject will be identified, including those observed outside of the monitoring planned by this ICP.

Complications may also be grouped according to their etiology. In all cases, the causal link with the device under investigation will be studied.

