### B. DATA DESCRIPTION

Demographic **data** of the included population and surgery, as well as endpoints and safety data, will be presented descriptively:

- Discrete qualitative and quantitative data will be summarized by their number, percentages, and percent confidence interval for each modality;
- Continuous quantitative data will be summarized by their mean, standard deviation, mean confidence interval, median, minimum and maximum.

**Clinical data** will be analyzed before and after surgery at each follow-up visit (functional measures) when available, including in terms of HHS and SHO-12 functional score if available, calculating score changes between preoperative and follow-up states. The confidence interval of the observed differences will make it possible to quantify the improvement or deterioration of the clinical status.

**Radiological data** will be analyzed before and after surgery at the follow-up visit. X-rays will document possible cases of complications (causal link with the bone defect), and provide information in terms of osseointegration/bone reconstruction.

Failure and revision rates will be analyzed by a Kaplan-Meier survival curve, with any revision surgery with removal or change of the SAGITTA EVL-R rod and/or locking keys as the inflection point. If several causes are identified, specific survival rates can be calculated.

The safety data related to the medical device will be presented throughout the duration of the follow-up. The complications observed can be grouped according to the data describing them provided and their etiology.

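### The only causality scale gives one grade for device or procedure and lists user error as a causal link, so it cannot yield the device-only grade that the safety outcome needs

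*Protocol*

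**What the plan says.** The target is the device. One secondary objective (section 5.C.ii) is: "Confirm the safety of these implants by studying any complications observed". The synopsis turns this into an outcome in which safety is "evaluated by the occurrence of adverse events related to the medical device". Section 6.A.iii (Complications) says that in all cases "the causal link with the device under investigation will be studied". Section 7.B says: "The safety data related to the medical device will be presented throughout the duration of the follow-up". The same section has safety data described by numbers, percentages and confidence intervals.

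Section 14.D supplies the only causality definitions, on one scale with four levels: Unbound, Possible, Probable and Causal link. Its opening sentence covers the device, a comparator and the investigation procedure in one judgement. Under Causal link it lists "Known side effect for this category of MD or this type of procedure", a site or organ criterion that either device or procedure can meet, and "SAE due to a user error". Section 14.F then treats every event not graded unrelated as an adverse effect. Section 14.A defines serious reactions to the device but has no procedure-related category.

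**The concern.** The outcome asks whether an event is related to the device. The scale asks whether it is related to the device or the procedure, and it stores one answer. The investigator assigns that grade when the event is recorded, so a later choice of table cannot fully undo the mixing.

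At stake is what the device-related safety summary describes. Revision hip surgery has complications of its own. If these share a grade with loosening or breakage of the stem, the summary describes the operation and the implant together, while the stated objective concerns the implant. An analyst would then have to decide afterwards, without a rule, which related events belong to the stem. The sponsor performs the analysis (synopsis; section 6.D.ii), so that rule is better fixed beforehand.

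**Working it through.** The protocol states no device-related complication rate, so there is no figure to reproduce. The check is textual.

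**Step 1: which procedure is meant?** Section 6.D.i adds only two questionnaires to routine care, the SHO-12 and the Harris score, and section 4.D identifies no specific risk of participation. Criteria about known side effects and affected organs can hardly refer to questionnaires. The sensible reading is the implantation surgery. This is an inference, but section 4.B supports it: it puts effects of the rods and of the surgery in one list. Haematoma, deep vein thrombosis, urinary infection and delayed healing stand there beside loosening and component breakage.

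**Step 2: does the scale separate device from procedure?** Section 14.D does not say whether one criterion is enough or all must be met, so both readings need testing.

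- *One criterion is enough.* A postoperative haematoma is a known effect of the surgery and so qualifies as Causal link. If the surgery is taken as another identified cause, it also qualifies as Unbound. The scale gives two opposite answers.
- *All criteria are needed.* Causal link would then require user error and a misdiagnosis result together, which no event of a non-diagnostic stem can satisfy. Unbound would require a site untouched by device or procedure, which a surgical-site complication cannot meet. That complication falls to Possible or Probable and still counts as related.

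Neither reading gives a device-only grade.

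**Step 3: what happens to the grade?** Under section 14.F, everything above Unbound is an adverse effect and goes on the dedicated form. Sections 6.A.iii and 7.B then want events linked to the device. The protocol text defines no other causality grade to use there.

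**Step 4: can the events be separated later?** Partly. All complications are recorded, and sections 6.A.iii and 7.B allow grouping by etiology. The grouping is optional, and no device/procedure rule is attached to it. An isolated urinary infection or a broken stem can be sorted by its description. Infection, fracture and dislocation can come from implant, surgery or both, and the description alone does not decide.

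**Step 5: do all the criteria fit this implant?** Reduction and reintroduction cannot be applied to a permanent stem; at most its removal is observed. A misdiagnosis by the device cannot occur, so its absence is true of every event, yet it is listed in support of Unbound.

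**The case against.** The best defence is that section 14.D is a reporting filter. Its heading and opening sentence concern what need not be notified to the sponsor, and a broad test is prudent for that purpose. Nothing says outright that this grade defines the analysed set, section 6.A.iii names the device alone, and the mapping of grades to tables may be left to an analysis plan. This stands in part. Reporting procedure-related events is no fault. But these are the only causality definitions in the protocol, and an analysis plan can use only the grades that were recorded.

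Four stronger readings are tempting, and the documents do not support them:

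- *The split is lost for good because it was never recorded.* Event descriptions are kept, and the reporting form (Appendix 4) and the CRF are not shown. Either may hold separate fields, although the protocol text does not require them.
- *A haematoma is graded exactly like a loosened stem.* This assumes that one criterion suffices, which section 14.D does not say. The same box also requires other causes to be excluded.
- *User error as a causal link contradicts section 4.B.* The note there, "In no case can these complications be attributed to SERF", follows a statement about the surgeon's responsibility. It does not grade causality. Section 14.B itself includes misuse among device defects, so recording user error is legitimate. The weakness is that it is merged into the same grade.
- *The rate is inflated by a stated amount.* Adding an assumed surgical rate to an assumed device rate only returns the assumptions. The documents give neither rate.

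**Conclusion.** The point holds as a weakness in how relatedness is graded. The safety outcome is device-related, and the only scale cannot give a device-only grade under either reading of its criteria. If it is applied as written and the summary rests on it, known complications of the implantation surgery can be counted with events of the stem, and only some can be separated afterwards.

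This rests on three assumptions: that procedure means the implantation surgery, that the grade feeds the safety summary because no other is defined, and that the unseen forms do not already split it. No size of effect can be derived from the documents. The outcome is secondary and descriptive, no test or success criterion depends on it (sections 7.D and 7.G), and the primary outcome, stem survival, is unaffected. It is a cheap improvement worth making.

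**What to change.** In section 14.D, and in the reporting form and CRF if they do not already do so:

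1. Grade each event twice on the same four levels: relation to the stem or locking keys, and relation to the index surgery.
2. Record user error as its own item, outside the criteria for the causal grade.
3. Say whether one criterion or all are needed for a grade.
4. Remove the reintroduction and misdiagnosis criteria, which do not fit this implant.

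In section 7.B, state that the device-related safety summary uses the device grade, name the levels that count as related, and show the procedure grade beside it. Notification to the sponsor can stay as broad as it is now.

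The cost is one extra tick per event, one extra table column and slightly more investigator time.
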